Study Protocol Title:

Elevation of the Fetal Buttocks Prior to External Cephalic Version

Study Sponsor:

AdventHealth Orlando

Principal Investigator:

Principal investigator: D. [name].

NCT04538261

IRB Approval Date:

11/23/2021

List of Abbreviations:

ECV	External Cephalic Version
FHR	Fetal heart rate
FDA	Food and Drug Administration
VAS	Visual Analog Scale
EMR	Electronic medical record

Introduction

This document is a protocol for a human research study. This study will be conducted in accordance with applicable federal regulations and institutional research policies and procedures.

Background Information and Scientific Rationale

Breech presentation, where the baby's buttocks or feet are presenting first, occurs in 3-4% of pregnancies after 37 weeks gestational age.¹ Options for patient with a term breech baby include cesarean delivery, attempted vaginal breech delivery, or attempted conversion from breech to a head first (cephalic) presentation using a procedure called external cephalic version (ECV). Breech vaginal deliveries are increasingly less common due to findings from a meta-analysis and systematic review that a planned cesarean delivery reduced both perinatal and neonatal death.

Many patients would like the opportunity to deliver vaginally, and in most cases those patients with a breech presentation after 36 weeks gestational age may be offered an ECV. ECV has varying rates of success depending on many factors, including whether the woman has had any prior pregnancies, the position of the baby, the amount of amniotic fluid, and whether the buttocks are deeply engaged in the pelvis.

Many obstetricians prefer to attempt ECV between 36-37 weeks gestational age because the success rate is similar to 34 weeks, but the baby is less likely to need neonatal intensive care if an emergent cesarean delivery is necessary. The success rate for nulliparous patients (those who have never delivered before) without spinal or epidural anesthesia is approximately 30%.

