Premature ruptured Membrane	Confirmed rupture of membranes	Rupture of membranes leading to immediate discontinuation of ECV procedure	Rupture of membranes leading to immediate labor induction	Life-threatening consequences; Cord prolapse resulting in fetal harm, defined as umbilical artery PH < 5 or admission to NICU	Cord prolapse resulting in fetal death
Other	Mild symptoms; intervention not indicated	Minimal, local or noninvasive intervention indicated	Medically significant but not immediately life-threatening	Life-threatening consequences; urgent intervention indicated	Death

- Severity of an adverse event will be determined and classified as described above by the Investigator.
- An unanticipated adverse device effect: any serious adverse effect on health or safety or any life-threatening problem or death caused by, or associated with, a device, if that effect, problem, or death was not previously identified in nature, severity, or degree of incidence in the investigational plan or application (including a supplementary plan or application), or any other unanticipated serious problem associated with a device that relates to the rights, safety, or welfare of subjects (21 CFR 812.3).
 - Sponsor will comply with FDA regulations 21 CFR 812.46 for monitoring requirements.

Relatedness/Causality of an adverse event will be determined and classified as described below by the Investigator.

Classification	Definition
Related	An event that results from the presence or performance (intended or otherwise) of the investigational device.
Unknown	An adverse event that cannot be determined to have a causal relationship with the device
Not Related	An adverse event that has been determined to not have a causal relationship with the device

Serious Adverse Event Reporting

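### The membrane-rupture severity row has no level for immediate cesarean, so the grade follows delivery route and may partly track whether the version worked

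*Combined protocol and SAP*

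**What the plan says.** The membrane-rupture row of the special-interest table (Adverse Event Reporting) grades by consequence:

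- Mild: "Confirmed rupture of membranes"
- Moderate: "Rupture of membranes leading to immediate discontinuation of ECV procedure"
- Severe: "Rupture of membranes leading to immediate labor induction"
- Serious, first column: "Life-threatening consequences; Cord prolapse resulting in fetal harm, defined as umbilical artery PH < 5 or admission to NICU"
- Serious, second column: "Cord prolapse resulting in fetal death"

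The rule for using the table is "Severity of an adverse event will be determined and classified as described above by the Investigator". In the vaginal hemorrhage and pelvic hematoma rows, the need for an invasive intervention is a Severe criterion.

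On delivery route, Background Information and Scientific Rationale says "Options for patient with a term breech baby include cesarean delivery". The same sentence goes on to attempted vaginal breech delivery and to version, and the section describes vaginal breech birth as declining. The section on vulnerable populations expects better version success to lower the risk of cesarean. The protocol does not say how a rupture is managed after a successful or a failed version.

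**The concern.** A rupture that leads straight to cesarean, without life-threatening consequences or cord prolapse with fetal harm, fits none of the upper levels. It falls to Moderate if it ended the version attempt, and otherwise to Mild. A rupture that leads to induction is Severe. Surgery therefore ranks below induction in this row, although invasive intervention ranks as Severe in two neighbouring rows. This looks like an omission rather than a chosen scale.

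The omission matters for comparing arms because induction is more natural when the fetus is head-down and cesarean when it is still breech. A grade that depends on delivery route then depends partly on the primary outcome. If the device works, its arm could show more Severe ruptures with no difference in the number of ruptures or in how many needed immediate delivery.

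Rupture is one of four named special-interest events. Safety review is planned after the first 10 randomized subjects and every 20 thereafter, without a DSMB, so one or two events could colour a review. The grader is the investigator, who is unblinded once the version is completed (Study Visits, Visit 2). An event with no matching level leaves that grader to improvise.

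**Working it through.** **Inputs.** Success rates of 49% (control) and 73.5% (device), and 76 women enrolled per arm, come from Sample Size Determination. The rates belong to a calculation that reproduces. The usual two-proportion formula (two-sided 5%, 80% power) gives 61 per group, and with continuity correction 69, as stated; 69 × 1.10 = 76. The special-interest table itself contains no figures. The documents give neither a rupture rate nor the chance of induction after rupture, so both are assumptions below.

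**Share of ruptures graded Severe.** Let s be the success rate, a the chance of immediate induction after rupture with a turned fetus, and b the same chance with a breech fetus. If rupture is equally common in both arms and independent of success, the Severe share is s × a + (1 − s) × b.

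| a / b | Control | Device | Ratio |
|---|---|---|---|
| 100% / 0% (extreme) | 0.49 | 0.735 | 1.5 |
| 80% / 20% | 0.49 × 0.8 + 0.51 × 0.2 = 0.494 | 0.735 × 0.8 + 0.265 × 0.2 = 0.641 | 1.3 |
| 50% / 50% | 0.50 | 0.50 | 1.0 |

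**Ruptures that themselves stop the version.** The Moderate level anticipates these. If a share q of ruptures ends the attempt without success, and those women are not induced, the extreme-case shares become (1 − q) × 49% and (1 − q) × 73.5%. At q = 0.5 they are 24.5% and 36.8%. At q = 1 both are zero. For any q below 1 the ratio stays at 1.5, but the shares and counts shrink.

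**Expected Severe ruptures, extreme case with q = 0.** The count is 76 × rupture rate × Severe share.

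| Assumed rupture rate | Control | Device | Difference |
|---|---|---|---|
| 1% | 0.37 | 0.56 | 0.19 |
| 2% | 0.74 | 1.12 | 0.37 |
| 5% | 1.86 | 2.79 | 0.93 |

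At an assumed 10% rate the counts would be 3.72 and 5.59.

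**What one trial would show.** At a 2% rate in the extreme case, binomial counts give the device arm more Severe ruptures with probability 0.44, a tie with 0.31, and fewer with 0.24. The approximate power to detect the artefact is about 6% at a 5% rupture rate and 9% at 10%.

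**After the change.** If Severe covers immediate delivery by either route, the expected ratio at equal rupture rates is 1.0, provided immediate delivery is equally likely at either presentation.

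**The case against.** A reader might infer that the severity comparison is biased against the device arm, with a 1.5-fold excess of Severe ruptures. The documents do not support that. It needs equal rupture rates, independence of rupture from success, immediate delivery after every rupture, and a strict split of induction when turned and cesarean when breech. None of these is stated. The background section also lists attempted vaginal breech delivery, and the Moderate level describes ruptures that can themselves cause failure.

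The consequences are also limited:

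- The SAP names no between-arm test of adverse event grades.
- Seriousness is defined by outcomes such as hospitalization, and the stated reporting to the FDA and IRB turns on seriousness and relatedness, not on this column.
- Rupture within an hour, delivery within an hour, induction and cesarean are each recorded without a grade.

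All of this stands, and it reduces the point to a small one. It does not supply the missing level. The Other row has a broad Severe criterion ("Medically significant but not immediately life-threatening"), but it is written for events without a row of their own, and rupture has one.

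A further objection is that immediate delivery is itself a management decision that may vary with presentation, so the reworded grade would not be fully neutral. That also stands, and it is why the fix has a second part.

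**Conclusion.** The gap in the table is plain on the text and needs no assumption: rupture leading to uncomplicated immediate cesarean grades Mild or Moderate, while rupture leading to induction grades Severe.

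The link to version success is plausible but conditional. If ruptures are equally common in both arms and independent of success, and induction is more likely after a turned than a breech fetus, somewhat more Severe ruptures would be expected in the more successful arm. The ratio is 1.3 at 80%/20% and 1.5 at most, falling to 1.0 where induction is equally likely. At assumed rupture rates of 1% to 5% this is less than one event between arms, so the direction seen in one trial would owe much to chance.

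The effect is confined to any tabulation of severity and to what the safety reviewers make of it. The primary analysis, the planned secondary tests, the serious adverse event rules and the sample size are untouched. This is a minor correction, worth making because it is cheap.

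**What to change.** 1. Reword the Severe level of this row so that it does not depend on route: *membrane rupture that leads to immediate delivery, by labor induction or cesarean*. Leave the other levels of the row as they are.
2. Make any between-arm comparison of rupture on the ungraded yes/no item already collected (rupture within 1 hour of the procedure, under Procedural Outcomes), read as including ruptures during the attempts. Use the grades for description only.

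The cost is a few words in one table cell and one sentence in the analysis plan. Ruptures already graded can be regraded from the induction, cesarean and timing data that the trial records. The change affects how an event is classified, not how any woman is managed.
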